**CONFIDENTIAL DOCUMENT**

This document contains confidential information, which is the property of Smith & Nephew, Inc. Do not copy, disclose, or circulate without written authorization from the appropriate Smith & Nephew personnel

- 10. Assess the ease of applying the dressing (see Section 9.5.7), including remains in place and repositioning (if applicable).
- 11. Instruct the subject to carefully follow the ulcer care instructions until the next dressing change and provide information concerning arrangements for future study visits.
- 12. Record the total time that the subject spent at the visit (start to finish of ulcer care procedures).
- 13. If any AE or DevD are observed or reported after application of study product, they must be reported as instructed in Section 12 (Adverse Events and Device Deficiencies).

#### **9.2.4 Visit 2 (Day 21 ± 3 days) and Visit 3 (Day 42 ± 4 days)**

Visits 2 and 3 will consist of an on-site visit. These visits should coincide with the normal timing of dressing changes, i.e. seven (7) days or fewer for ALNB.

Subjects who have already had their treatment discontinued/been withdrawn from treatment and no longer require a dressing change shall be followed up either by an on-site visit or by telephone. In such cases, the main purpose will be to collect CWIS outcome data and any data related to AE (if applicable).

- 1. Question subjects regarding any changes in health or concomitant treatment.
- 2. All subjects must complete the CWIS, including those withdrawn from treatment unless they have been withdrawn from the study.

Give the subject a printed copy of the CWIS and allow sufficient time to complete it. Assist with completion if asked. For any subject followed up by telephone, read the complete CWIS and record the subject's responses accurately. Ensure that the subject has completed the CWIS appropriately. A single valid response should be recorded for each item.

NOTE: subjects who cannot read/write may have the CWIS read aloud to them and the subject's responses recorded. Ensure this process is noted in the source documents.

3. Ask the subject to assess the comfort of wearing the dressing since the last visit (see Section 9.5.8).
4. Assess the movement of the dressing (see Section 9.5.9).
5. Remove the old dressing and inspect the ulcer. Complete an ulcer assessment (see Section 9.5.1).

*Notes: 1) A full ulcer assessment is not necessary if the subject has already been discharged or withdrawn from treatment.*

*2) Not applicable if this visit is completed via a phone call.*

6. Assess the level of pain experienced by the subject when the dressing is removed (see Section 9.5.6).
7. Assess the ease of dressing removal, leakage, and absorption under compression (see section 9.5.10)
8. Take a photograph of the ulcer, showing the ruler as supplied. Record any debridement and the method of debridement, and take a photograph of the ulcer immediately prior to and following debridement.

Photograph the used dressing on both sides, together with any secondary dressing.

Note: Photographs are not necessary if the subject was discharged or withdrawn from treatment at a previous visit.

9. Redress the ulcer, if clinically indicated, using an appropriate dressing according to group allocation:

For subjects allocated to the experimental group, apply ALNB as supplied for use in the study, cutting the dressing to size if required and securing with a suitable secondary dressing.

For subjects allocated to SC apply a suitable protective dressing, other than ALLEVYN LIFE/ALNB.

10. Record details of all dressings used for all subjects, (e.g. brand, size, etc.) as well as any treatment applied underneath the dressing, such as Durafiber or Intrasite gel.

For subjects randomized to ALNB, record whether or not the dressing was cut to a smaller size.

11. Assess the ease of applying the dressing (see Section 9.5.7), including remains in place and repositioning (if applicable).

12. Instruct the subject to carefully follow the ulcer care instructions until the next dressing change and provide information concerning arrangements for future study visits.

13. Record the total time that the subject spent at the visit (start to finish of ulcer care procedures).

14. If any AE or DevD are observed or reported, they must be recorded as instructed in Section 12 (Adverse Events and Device Deficiencies).

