### 6.1.2 Comparator Products

Subjects allocated to the comparator arm of the study shall receive SC, defined as any protective wound dressing(s) which, in the opinion of the Investigator, would be beneficial in treating the wound, other than:

- variants of ALLEVYN
- topical antimicrobials, such as Acticoat™, Iododsorb™, silver products, etc.
- negative pressure wound therapy

Standard care should correspond as closely as possible to normal clinical practice, and dressings used routinely within each individual research site.

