#### **9.2.5 End of Study Visit – Week 12 (84 ± 4 days)**

The End of Study Visit will consist of an on-site visit. This should coincide with the normal timing of dressing changes, i.e. seven (7) days or fewer for ALNB.

Subjects who have already had their treatment discontinued/been withdrawn from treatment shall be followed-up either by an on-site visit or by telephone. Obtain information about adverse events and responses to the CWIS.

1. Question subjects regarding any changes in health or concomitant treatment.
2. All subjects must complete the CWIS, including those withdrawn from treatment unless they have been withdrawn from the study.

Give the subject a printed copy of the CWIS and allow sufficient time for them to complete it. Assist with completion if asked. For any subject followed up by telephone (see above), read the complete CWIS and record the subject's responses accurately. Ensure that the subject has completed the CWIS appropriately. A single valid response should be recorded for each item of the CWIS.

**NOTE:** Subjects who cannot read/write may have the CWIS read aloud to them and the subject's responses recorded. Ensure this process is noted in the source documents.

3. Ask the subject to assess the comfort of wearing the dressing since the last visit (see Section 9.5.7).
4. Assess the movement of the dressing (see Section 9.5.9).
5. Remove the old dressing and inspect the ulcer. Complete an ulcer assessment (see Section 9.5.1).

***Note:*** *A full ulcer assessment is not necessary if the subject has already been discharged or withdrawn from treatment.*

6. Assess the level of pain experienced by the subject when the dressing is removed. (see Section 9.5.6).
7. Assess the ease of dressing removal, leakage, and absorption under compression (see section 9.5.10)

8. Take a photograph of the ulcer, showing the ruler as supplied. Record any debridement and the method of debridement, and take a photograph of the ulcer immediately prior to and following debridement.

Photograph the used dressing on both sides, together with any secondary dressing.

Note: Photographs are desirable, but not necessary if the subject has been discharged or withdrawn from treatment.

9. Exit the subject from the study.

The subject will be returned to SC and the Investigator will advise him/her of subsequent therapy and/or procedures necessary for their medical condition.

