Do not apply any dressing supplied by S&N for use within the study, as the study treatment is being discontinued.

11. Record details of any new dressings applied and complete all remaining items in the eCRF.

12. Instruct the subject on the need to continue as a participant in the study, providing important information about their health and quality of life, until the End of Study Visit ( $84 \pm 4$  days from Visit 1).

13. If ongoing treatment is clinically indicated, continue to provide the subject with SC for the remainder of the study.

14. Record the total time that the subject spent at the visit (start to finish of ulcer care procedures).

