If a subject has missing data for any values for length, width or depth of the wound at a particular visit, and has at least one post-baseline score, then the LOCF method will be used. The only exception to this is when missing values occur and the ulcer is healed, in which case 0cm (length/ width) or 0mm (depth) shall be imputed for all missing measurements in the statistical analysis.

Ulcer healed status

CONFIDENTIAL AND PROPRIETARY

This document contains information that is confidential and proprietary to Smith & Nephew PLC and Smith & Nephew, Inc. and is intended for use only by Smith & Nephew and its manufacturer. It shall not be reproduced or copied in whole or in part, nor shall the contents be disclosed by any means without prior written permission from Smith & Nephew, nor shall anyone make any use of it that is contrary to the expressed or implied wishes of Smith & Nephew

Statistical Analysis Plan	 Number: CT1603ALF ST: 1005 Version: 1.0, 27-Jul-2018 Page: 15 of 27
A Pilot Randomized Controlled Trial to Evaluate an Advanced Borderless Dressing (ALLEVYN™ LIFE Non-Bordered) in the Treatment of Chronic Ulcers	

If the ulcer healed status is missing at a particular assessment and the ulcer was marked as healed at the previous assessment then the ulcer should be classified as healed.

If the ulcer healed status is missing at a particular assessment and the ulcer was not marked as healed at the previous assessment then the ulcer should not be classified as healed. If the baseline ulcer healed status is missing then this should also be implemented as not healed.

In cases where the wound is recorded as healed in the investigators opinion the following imputations will be made if missing values are present: Signs of critical colonisation or infection = No. Level of Exudate = None.

Healthcare resource use

If any of the healthcare resource data is missing then no missing data implementation will be used.

Dressing Change

If any of the dressing change data from the exploratory endpoints is missing then no missing data implementation will be used.

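### The full ulcer assessment is optional after treatment stops and the last healed status is carried forward, so the secondary healing comparison can be biased by an amount and in a direction the documents do not settle

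*Protocol*

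**What the plan says.** Protocol 9.2.6 keeps subjects who stop study treatment in the study to week 12, but the visit instructions reduce what is collected from them.

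- **Assessment.** In protocol 9.2.4 (weeks 3 and 6) a note to step 5 says that "A full ulcer assessment is not necessary if the subject has already been discharged or withdrawn from treatment". Sections 9.2.5 (week 12) and 9.2.6 carry the same note. Photographs after withdrawal are not required either.
- **Contact.** At weeks 3 and 6, subjects who have stopped treatment "and no longer require a dressing change shall be followed up either by an on-site visit or by telephone". At week 12, subjects withdrawn from treatment "shall be followed-up either by an on-site visit or by telephone", with no condition about dressings. The purpose given for these contacts is CWIS and adverse event data.
- **Schedule.** Protocol Table 9.2-1 and SAP Table 3.1 mark an ulcer assessment at every key visit, with no exception for these subjects.
- **Imputation.** SAP 7.3 deals with a missing healed status in two ways: if "the ulcer was not marked as healed at the previous assessment then the ulcer should not be classified as healed"; and if "the ulcer was marked as healed at the previous assessment then the ulcer should be classified as healed". Missing dimensions take the last post-baseline value, or 0 if the ulcer is healed. Bates-Jensen items are also carried forward.
- **Stopping.** Protocol 7.6 gives one list of reasons for both arms, which includes closure of the reference ulcer and a warranted change of treatment. SC is defined in 6.1.2 as "any protective wound dressing(s) which, in the opinion of the Investigator, would be beneficial in treating the wound", apart from ALLEVYN variants, topical antimicrobials and negative pressure therapy. After discontinuation, 9.2.6 says: "If ongoing treatment is clinically indicated, continue to provide the subject with SC for the remainder of the study".
- **Use.** Healed status and ulcer dimensions at weeks 3, 6 and 12 are secondary endpoints compared between groups (SAP 5.3) and modelled in SAP 7.11.

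**The concern.** The full analysis set is said to follow the intention-to-treat principle, yet ulcer outcomes may stop being observed when treatment stops. The imputation rule then supplies a value that looks like an observation. An ulcer that heals after an unhealed stop can enter the model as open. An ulcer that closes (itself a reason to stop) and later reopens can enter as healed with area 0.

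If stopping differs between arms, so does this misclassification. There is reason to expect a difference. Replacing ALNB with another protective dressing ends ALNB treatment. Replacing one protective dressing with another normally leaves an SC subject on SC, and no section says what stopping SC means.

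Protocol 8.2 wants effect estimates from this pilot to guide a later full-scale trial. A systematic error in the healing estimates would be carried into that planning.

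**Working it through.** The plan states no healing rate, stopping rate or power, so there is no figure on this point to reproduce. The allocation does reproduce: 40 × 5/8 = 25 ALNB and 40 × 3/8 = 15 SC.

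**Step 1. Where status can be missing.**

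| Subject withdrawn from treatment | Weeks 3 and 6 | Week 12 |
|---|---|---|
| Ulcer still needs dressing changes | Telephone option not offered; full assessment optional | Telephone allowed; full assessment optional |
| No dressing change needed | Site or telephone; full assessment optional | Site or telephone; full assessment optional |

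The notes do not say which parts of the assessment remain when the full one is waived. Protocol 9.5.1 lists healing status within the ulcer assessments.

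**Step 2. Bias from unrecorded healing.** Let dA and dC be the shares of the ALNB and SC arms that stop with an open ulcer and have no later status recorded. Let q be the share of those who then heal by week 12, taken as equal in the two arms. With equal true healing:

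bias in recorded healing (ALNB − SC) = −(dA − dC) × q

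All rates below are assumptions, with q from 0.2 to 0.5.

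| dA / dC | Calculation | Bias (percentage points) |
|---|---|---|
| 10% / 10% | −0.00 × q | 0 (each arm understated by 2 to 5) |
| 20% / 20% | −0.00 × q | 0 (each arm understated by 4 to 10) |
| 10% / 5% | −0.05 × 0.2 to −0.05 × 0.5 | −1.0 to −2.5 |
| 20% / 5% | −0.15 × 0.2 to −0.15 × 0.5 | −3.0 to −7.5 |
| 30% / 5% | −0.25 × 0.2 to −0.25 × 0.5 | −5.0 to −12.5 |

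**Step 3. Unrecorded reopening.** This acts the other way within an arm. Each missed reopening overstates healing by 1/25 = 4.0 points in ALNB or 1/15 = 6.7 points in SC. It applies to closures in both arms, so the sign of the net bias is not fixed.

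**Step 4. Random error for comparison.** For a simple difference in proportions at one visit, SE = √[p(1 − p)(1/25 + 1/15)], and 1/25 + 1/15 = 0.1067.

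| True healing p | SE (points) | 95% half-width, 1.96 × SE (points) |
|---|---|---|
| 30% | √(0.21 × 0.1067) = 15.0 | 29.3 |
| 40% | √(0.24 × 0.1067) = 16.0 | 31.4 |
| 50% | √(0.25 × 0.1067) = 16.3 | 32.0 |

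Every illustrated bias is smaller than one standard error.

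**The case against.** The case for leaving the plan alone has substance.

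- The waiver is permissive and names no arm. SC subjects can also stop, for example for an adverse event or a change to a product outside the SC definition.
- Open ulcers are mostly still seen. Telephone contact at weeks 3 and 6 is only for subjects who need no dressing change. Protocol 6.2.2 expects dressing changes at the site, and 9.2.7 records any site visit due to the reference ulcer as a routine dressing change, which under 9.2.3 includes an ulcer assessment.
- The SAP refers to the previous assessment, not the previous key visit. Healing seen at a routine visit could therefore be carried forward as healed.
- The CWIS form in protocol 21.2 has a healed/not healed box, and retained subjects must complete the CWIS. Each contact also asks about changes in health and treatment, which could reveal a reopening.
- This is a feasibility-sized pilot, and these are secondary endpoints.

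Most of this stands, and it narrows the gap: status is carried forward only where it was not recorded. It does not close the gap. The SAP names neither routine-visit data nor the CWIS box as a source for the week 3, 6 and 12 models, and it does not define the previous assessment. At week 12 a subject with an open ulcer may be followed by telephone alone. The only analysis without imputation (SAP 7.9) concerns CWIS-PSDL.

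**Conclusion.** The waiver notes and the study plan tables disagree. Together with SAP 7.3, the notes allow healing after an unhealed stop, or reopening after closure, to be misrecorded in endpoints compared between arms. The healing comparison can therefore be biased.

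A reader might go further and infer that outcome collection ends in the ALNB arm only, so that ALNB healing is understated by 4, 8 or 12 points when 10%, 20% or 30% of ALNB subjects stop. The documents do not support that. The stop list is common to both arms, and more frequent stopping in ALNB is an inference from the breadth of SC. Those figures come from s × 0.40, where s is the share of ALNB subjects stopping. They assume no SC stopping, no reassessment of anyone, and 40% later healing among ulcers still open at the stop. If 40% heal overall and half of that healing comes before the stop, later healing is 0.20/0.80 = 25%, and the figures fall to 2.5, 5 and 7.5 points even with no SC stopping.

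What can be said is conditional. The bias from unrecorded healing is zero if stopping and later healing are equal across arms. It is about −1 to −12.5 points under the assumed unequal rates, against a standard error of 15 to 16 points. Unrecorded reopening can push the result either way. The primary CWIS-PSDL endpoint is not affected, because subjects withdrawn from treatment must still complete the CWIS. The point is worth acting on because the remedy is cheap and the estimates are meant to inform a later trial.

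**What to change.** **Protocol.** Reconcile the notes in 9.2.4, 9.2.5 and 9.2.6 with Table 9.2-1 and SAP Table 3.1. Require healed status at weeks 3, 6 and 12 for every subject still in the study, whatever the treatment status, by a telephone question if the ulcer is not seen. Require dimensions and Bates-Jensen items whenever the ulcer is seen on site.

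**SAP.** In 7.3, use observed status first, including status from routine visits; define the previous assessment; and impute only when status cannot be obtained. In 7.11, report the number of imputed healed statuses by arm and visit, and add an observed-data sensitivity analysis for healing.

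**Cost.** Wording changes, and a few extra minutes at visits and calls that already take place. Status reported by telephone is less reliable than examination, so its source should be recorded.

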#### **9.2.5 End of Study Visit – Week 12 (84 ± 4 days)**

The End of Study Visit will consist of an on-site visit. This should coincide with the normal timing of dressing changes, i.e. seven (7) days or fewer for ALNB.

Subjects who have already had their treatment discontinued/been withdrawn from treatment shall be followed-up either by an on-site visit or by telephone. Obtain information about adverse events and responses to the CWIS.

1. Question subjects regarding any changes in health or concomitant treatment.
2. All subjects must complete the CWIS, including those withdrawn from treatment unless they have been withdrawn from the study.

Give the subject a printed copy of the CWIS and allow sufficient time for them to complete it. Assist with completion if asked. For any subject followed up by telephone (see above), read the complete CWIS and record the subject's responses accurately. Ensure that the subject has completed the CWIS appropriately. A single valid response should be recorded for each item of the CWIS.

**NOTE:** Subjects who cannot read/write may have the CWIS read aloud to them and the subject's responses recorded. Ensure this process is noted in the source documents.

3. Ask the subject to assess the comfort of wearing the dressing since the last visit (see Section 9.5.7).
4. Assess the movement of the dressing (see Section 9.5.9).
5. Remove the old dressing and inspect the ulcer. Complete an ulcer assessment (see Section 9.5.1).

***Note:*** *A full ulcer assessment is not necessary if the subject has already been discharged or withdrawn from treatment.*

6. Assess the level of pain experienced by the subject when the dressing is removed. (see Section 9.5.6).
7. Assess the ease of dressing removal, leakage, and absorption under compression (see section 9.5.10)

8. Take a photograph of the ulcer, showing the ruler as supplied. Record any debridement and the method of debridement, and take a photograph of the ulcer immediately prior to and following debridement.

Photograph the used dressing on both sides, together with any secondary dressing.

Note: Photographs are desirable, but not necessary if the subject has been discharged or withdrawn from treatment.

9. Exit the subject from the study.

The subject will be returned to SC and the Investigator will advise him/her of subsequent therapy and/or procedures necessary for their medical condition.

10. Record the total time that the subject spent at the visit (start to finish of ulcer care procedures).

11. If any AE or DevD are observed or reported, they must be recorded as instructed in Section 12 (Adverse Events and Device Deficiencies).

### 9.2.6 Treatment Discontinuation

A subject may be withdrawn from treatment early and discharged from care (see Sections 7.6 and 9.3) prior to follow-up at Visit 2, Visit 3, or the End of Study Visit. However, these subjects will still be retained as active study participants, even though their study treatment has ended. When this occurs, the subject will continue as an active participant for the remainder of the twelve (12) week study period, completing all remaining study visits (either by attending site appointments or by telephone if necessary), to gather complete CWIS data.

1. Question subjects regarding any changes in health or concomitant treatment.
2. Give subject given a copy of the CWIS and allow sufficient time for them to complete it. Assist with completion if asked. For any subject followed up by telephone (see above), read the complete CWIS and record the subject's responses accurately. Ensure that the subject has completed the CWIS appropriately. A single valid response should

be recorded for each item of the CWIS.

NOTE: subjects who cannot read/write may have the CWIS read aloud to them and the subject's responses recorded. Ensure this process is noted in the source documents.

3. Ask the subject to assess the comfort of wearing the dressing since the last visit (see Section 9.5.8).
4. Assess the movement of the dressing. (see Section 9.5.9).
5. Remove the old dressing and inspect the ulcer. Complete an ulcer assessment (see Section 9.5.1).

*Notes: 1) A full ulcer assessment is not necessary if the subject has already been discharged or withdrawn from treatment.*

*2) Not applicable if this visit is completed via a phone call.*

6. Assess the level of pain experienced by the subject when the dressing is removed. (see Section 9.5.6).
7. Assess the ease of dressing removal, leakage, and absorption under compression (see section 9.5.10).
8. Take a photograph of the ulcer, showing the ruler as supplied. Record any debridement and method of debridement, and take a photograph of the ulcer immediately prior to and after debridement.

Photograph the used dressing on both sides, together with any secondary dressing.

9. If any AE or DevD are observed or reported, they must be recorded as instructed in Section 12 (Adverse Events and Device Deficiencies).

Photograph the dressing only if reporting a device deficiency.

10. Redress the ulcer, if clinically indicated, using an appropriate dressing.  
Do not apply any dressing supplied by S&N for use within the study, as the study treatment is being discontinued.

11. Record details of any new dressings applied and complete all remaining items in the eCRF.

12. Instruct the subject on the need to continue as a participant in the study, providing important information about their health and quality of life, until the End of Study Visit ( $84 \pm 4$  days from Visit 1).

13. If ongoing treatment is clinically indicated, continue to provide the subject with SC for the remainder of the study.

14. Record the total time that the subject spent at the visit (start to finish of ulcer care procedures).

